10.1.3.6 Other Laboratory Variables

Not applicable

10.1.3.7 Vital Signs

Vital signs (body temperature, systolic and diastolic BP, oxygen saturation, HR, RR, and pulse oximetry) will be recorded at the time points specified in the relevant Schedule of Assessments for Part A (Table 1), Part B (Table 2) and Part C (Table 3a inpatients and Table 3b outpatients).

In Part C, collected vital signs and SpO₂ levels will be analyzed as normal, mild, moderate, or severe according to the following definitions:

- Temperature:
 - Normal (no fever): <38°C
 - Mild: 38-39°C
 - Moderate: >39-40°C
 - Severe: >40°C
- Respiratory rate (breaths/min):
 - Normal: ≤30
 - Mild: 31-45
 - Moderate: 46-60
 - Severe: >60
- SpO₂ on Room Air (Oxygen Saturation)
 - Normal: >94%
 - Mild: >92-94%
 - Moderate: 90-92%
 - Severe: <90%

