Evaluation of Safety: For laboratory tests, ECG measures, and vital signs parameters, baseline will be defined as the last non-missing result before the first dose of IMP. Results at each visit will be summarised using the statistics: n (number of observations), mean, standard deviation (SD), median, minimum and maximum. In addition, change from baseline for all safety parameters will also be summarised by post-baseline visits.

Adverse events will be coded according to the Medical Dictionary for Regulatory Activities (MedDRA) dictionary. Summary tables of AEs will be based on TEAEs, defined as events starting, or worsening, after the first dose of IMP. Summaries by MedDRA System Organ Class (SOC) and Preferred Term will be provided for all TEAEs, all treatment-related TEAEs (with causality assessed as possibly, probably, or definitively related to IMP), all serious TEAEs and all TEAEs leading to early discontinuation from the study. Summary tables by maximum severity and maximum relationship will be presented.

Clinical:

RSV-related signs and symptoms will be summarised by duration (number [%] of subjects analysed, mean, median, SD, minimum, maximum). In addition, signs and symptoms will be summarised by highest level of severity by treatment group. Also, change from baseline will also be summarised for post-baseline visits. Baseline will be defined as the last non-missing result before the first dose of IMP.

RSV-related signs and symptoms will include, but are not limited to: respiratory rate, heart rate, wheezing retractions.

For Parts B and C:

Individual RSV symptoms will be summarised by frequency at each time point by treatment assignment. Individual RSV-related symptoms will be summarised, for subjects reporting a symptom at study start, for time to resolution (mean, median, SD, minimum and maximum times).

Time to improvement will be calculated for RSV-related signs and symptoms that are classified as moderate or severe during the course of the study and will be defined as the time from randomisation until no longer present (absent or mild).

The Overall Time to Improvement will be defined as the time from randomisation to the time that all RSV-related signs and symptoms are mild or absent. The overall time to improvement will be summarised for each treatment group by mean, median, SD, minimum and maximum and 95% confidence intervals.

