7.2 PART C: Objectives and Endpoints

Primary Objectives for Part C	Primary Endpoint

 • Evaluate the antiviral effects of RV521, compared to placebo, on nasopharyngeal shedding of RSV in infants hospitalised with RSV LRTI 	
 • Time-weighted average change from Baseline to Day 7 in RSV viral load measured in nasopharyngeal swabs by RT-qPCR.
Secondary Objectives for Part C	Secondary Endpoints

 • To evaluate virologic parameters derived from the RSV viral load as measured in nasopharyngeal swabs • CCI [REDACTED] 	
 • Virologic parameters derived from the RSV viral load as measured in nasal swabs include but are not limited to: 
 ○ Change from baseline in viral load (RT-qPCR and CBIA) at each time point ○ Time to below viral load quantification limit (RT-qPCR and CBIA) ○ Proportion of subjects with viral load below quantification limit (RT-qPCR and CBIA) at each timepoint throughout the study • CCI [REDACTED]

 To evaluate the clinical efficacy of multiple oral doses of RV521 in infants hospitalised with RSV LRTI Evaluate the safety and tolerability of RV521 given as a multiple dose regimen 	
 Time to resolution in RSV-related symptoms Time to improvement of RSV-related symptoms Reduction in severity of symptoms by RV521, compared to placebo, measured by a composite score over time Use of supplementary oxygen, including, but not limited to, duration and maximum level of O₂ provided Time to normalisation of respiratory rate Safety of RV521 compared to placebo assessed by incidences of AEs, discontinuations due to AEs, SAEs, and clinically significant changes in laboratory tests

Exploratory Endpoints (Part C)
	
 [REDACTED] [REDACTED] [REDACTED]

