10.1.2.2 Clinical Response Assessments

Clinical response will be measured by evaluation of the RSV signs and symptoms list (all Parts), RSV Clinical Scoring System (Parts A and B), the ReSVinet Score for Clinicians (Part C), and the adapted version of ReSVinet scale for parental use (Parts B and C). In addition, CCI [REDACTED] and time to normalisation of respiratory rate will be analysed in Part C. Details of how the clinical efficacy endpoints will be analysed, and by which scales, is briefly described in Section 11.1.5 and will be outlined in the Statistical Analysis Plan.

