11.1.5 Clinical Response Variables

Two scales of clinical response will be considered, the RSV Clinical Scoring System and the ReSViNet scale. In Parts A and B, clinicians will complete the RSV Clinical Scoring System, which gives a score from 0 to 12. In Part C, the ReSVinet scale for clinicians, which gives a score from 0 to 20 will be completed. For parental assessment of clinical response, the Adapted Version of ReSVinet Scale for Parental Use, which gives a score from 0 to 20 will be analysed.

Both the RSV Clinical Scoring System and the ReSViNet scale for clinicians will be summarised by treatment (dose level) and time point. In addition, for post-dose assessments, change from baseline will also be summarised, where baseline is the last non-missing score prior to the first dose of study drug. For Parts B and C, comparisons will be made between RV521 and placebo using analysis of covariance models.

In addition the score for the RSV Clinical Scoring System will be categorised as:

- Mild – scores ≤ 5
- Moderate – scores > 5 and < 9
- Severe – scores ≥ 9

The number and percent of subjects with mild, moderate and severe assessments will be summarised by treatment (dose level and time point).

The Adapted Version of ReSVinet Scale for Parental Use score will be summarised by treatment (dose level) and time point. In addition, for post-dose assessments, change from baseline will also be summarised, where baseline is the last non-missing score prior to the first dose of study drug. For Part B and Part C, comparisons will be made between RV521 and placebo using analysis of covariance models.

Individual RSV-related signs and symptoms ([Appendix 17.4](#)) at each visit will be summarised by treatment (dose level). Quantitative variables will be summarised using the statistics number of observations (n), mean, SD, median, minimum and maximum values. In addition, change from baseline will also be summarised for post-baseline visits. Baseline will be defined as the last non-missing result before the first dose of study medication. Qualitative variables will be summarised using n (number of subjects), absolute numbers and relative frequencies (%) per class.

Time to improvement will be calculated for RSV-related signs and symptoms that are classified as moderate or severe during the course of the study and will be defined as the time from randomisation until no longer present (absent) or mild.

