The Overall Time to Improvement will be defined as the time from randomisation to the time that all RSV-related signs and symptoms are mild or absent. The overall time to improvement will be summarised for each treatment group by mean, median, SD, minimum and maximum and 95% confidence intervals.

Overall Time to Resolution of RSV-related signs and symptoms will be calculated from the time of randomisation to the time that they are no longer present (absent), and will be summarised and analysed as for Time to Improvement.

Treatment groups will be compared for differences in overall severity assessed by the composite symptom score on each day whilst hospitalised and at follow-up visits.

For Part C, time to resolution of symptoms will be compared between each dose level of RV521 and Placebo using a generalised Wilcoxon Rank test. Details of the analysis will be provided in the SAP.

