17.4 RSV-related Signs and Symptoms to be Collected

Temperature enter _____

Respiratory Rate enter _____

Coryza None Mild Moderate Severe

Cough None Mild Moderate Severe

Grunting with expiration None Present

Nasal flaring None Present

Retractions None Mild Moderate Severe

Wheezing None Mild Moderate Severe

SpO₂ on room air enter _____

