17.6 ReSVinet Scale for Clinicians

Item	0 points	1 points	2 points	3 points
1 Feeding intolerance	No	Mild Decreased appetite and/or isolated vomits with cough.	Partial Frequent vomits with cough, rejected feed but able to tolerate fluids sufficiently to ensure hydration.	Total Oral intolerance or absolute rejection of oral feed, not able to guarantee adequate hydration orally. Required nasogastric and/or intravenous fluids
2 Medical intervention	No	Basic Nasal secretions aspiration, physical examination, trial of nebulized bronchodilators, antipyretics.	Intermediate Oxygen therapy required. Complementary exams were needed (chest X-rays, blood gases, hematimetry...). Maintained nebulized therapy with bronchodilators.	High Required respiratory support with positive pressure (either non-invasive in CPAP, BiPAP or high-flow O ₂ ; or invasive through endotracheal tube).
3 Respiratory difficulty	No	Mild Not in basal situation but does not appear severe. Wheezing only audible with stethoscope, good air entrance. If modified Wood Downes, Wang score or any other respiratory distress score is applied, it indicates mild severity.	Moderate Makes some extra respiratory effort (intercostal and/or tracheosternal retraction). Presented expiratory wheezing audible even without stethoscope, and air entrance may be decreased in localized areas. If modified Wood Downes, Wang score or any other respiratory distress score is applied, it indicates moderate severity.	Severe Respiratory effort is obvious. Inspiratory and expiratory wheezing and/or clearly decreased air entry. If modified Wood Downes, Wang score or any other respiratory distress score is applied, it indicates high severity.
4 Respiratory frequency	Normal < 2 m: 40–50 bpm 2–6 m: 35–45 bpm 6–12m: 30–40 bpm 12–24m:25–35 bpm 24–36m: 20–30 bpm	Mild or occasional tachypnea Presented episodes of tachypnea, well tolerated, limited in time by self-resolution or response to secretion aspiration or nebulization.	Prolonged or recurrent tachypnea Tachypnea persisted or recurred despite secretion aspiration and/or nebulization with bronchodilators.	Severe alteration Severe and sustained tachypnea. Very superficial and quick breath rate. Normal/low breath rate with obvious increased respiratory effort and/or mental status affected. Orientative rates of severe tachypnea: < 2 m: > 70 bpm 2–6 m: > 60 bpm 6–12m: >55 bpm 12–24m: >50 bpm 24–36m: >40 bpm

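### Part C grades respiratory rate with one cut-off for all ages (normal up to 30), which conflicts with the numeric age-specific normal ranges of the ReSVinet clinician scale used in the same part, while the respiratory-rate normalisation endpoint is left undefined

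*Protocol*

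**What the plan says.** Protocol Section 10.1.3.7 (Vital Signs) states that in Part C vital signs and SpO₂ "levels will be analyzed as normal, mild, moderate, or severe according to the following definitions". For respiratory rate the bands are: normal ≤30, mild 31-45, moderate 46-60, severe >60. There is no age term, although Part C enrols from 1 to 36 months and stratifies at 6 months.

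Protocol Appendix 17.6, the ReSVinet Scale for Clinicians completed in Part C (Section 11.1.5), gives normal rates by age: 40-50 under 2 months, 35-45 at 2-6, 30-40 at 6-12, 25-35 at 12-24 and 20-30 at 24-36 months. It also gives "Orientative rates of severe tachypnea": above 70, 60, 55, 50 and 40 respectively.

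On the endpoints:
- The Synopsis says "RSV-related signs and symptoms will include, but are not limited to: respiratory rate" and goes on to name heart rate and other signs. Appendix 17.4 collects the rate as a bare number ("Respiratory Rate enter").
- Section 11.1.5 applies time to improvement to "RSV-related signs and symptoms that are classified as moderate or severe during the course of the study", and defines the overall version as "the time from randomisation to the time that all RSV-related signs and symptoms are mild or absent". Overall resolution requires every sign to be absent.
- Section 7.2 lists "Time to normalisation of respiratory rate" as a Part C secondary endpoint. Neither document defines it.
- Section 10.1.2.2 leaves to the SAP the "Details of how the clinical efficacy endpoints will be analysed, and by which scales".

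**The concern.** One measurement in one part of the trial has two numeric definitions of normal, and for the youngest children they do not overlap. The concern is what happens when a programmer has to derive the clinical endpoints. A rate recorded only as a number must be turned into absent, mild, moderate or severe before it can enter an improvement or resolution rule, and into normal before it can normalise. Section 10.1.3.7 is the only place that says numerically how a Part C rate is analysed as normal.

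If that rule is used, a child under 6 months who has recovered to a ReSVinet-normal rate is still graded abnormal. Overall resolution needs all signs absent, so one sign can block the event, and under the censoring rule in SAP Section 8.3 a child who never meets it is censored at the last recorded assessment. At stake are events, and hence sensitivity, on three Part C secondary endpoints: time to resolution, time to improvement and time to normalisation of respiratory rate.

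**Working it through.** The plan states no figure to reproduce here. The check is to grade each whole-number rate in the Appendix 17.6 normal ranges with the Section 10.1.3.7 bands.

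**Counts.** For a normal range from a to b, there are b − a + 1 = 11 whole-number rates in every band.
- Graded normal (≤30): max(0, min(b, 30) − a + 1)
- Graded mild (31-45): max(0, min(b, 45) − max(a, 31) + 1)
- Graded moderate (46-60): max(0, b − max(a, 46) + 1), since no b exceeds 60

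| Age | 17.6 normal range | Graded normal | Graded mild | Graded moderate |
|---|---|---|---|---|
| <2 months | 40-50 | 0 of 11 | 45 − 40 + 1 = 6 | 50 − 46 + 1 = 5 |
| 2-6 months | 35-45 | 0 of 11 | 45 − 35 + 1 = 11 | 0 |
| 6-12 months | 30-40 | 30 − 30 + 1 = 1 of 11 | 40 − 31 + 1 = 10 | 0 |
| 12-24 months | 25-35 | 30 − 25 + 1 = 6 of 11 | 35 − 31 + 1 = 5 | 0 |
| 24-36 months | 20-30 | 30 − 20 + 1 = 11 of 11 | 0 | 0 |

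Below 6 months the lowest ReSVinet-normal rate is 35, already above the cut-off of 30. Below 2 months, 46-50 is graded moderate, so it would fail improvement as well as resolution. These are counts of rates, not of children.

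**Upper end.** The orientative severe rates are >70, >60, >55, >50 and >40, against a single >60 in Section 10.1.3.7. They agree only at 2-6 months.
- Under 2 months, 61-70 is graded severe but is not above the ReSVinet severe rate.
- At 6-12 months, 56-60 is above the ReSVinet severe rate but graded moderate; at 12-24 months the same holds for 51-60.
- At 24-36 months, 41-45 is above the ReSVinet severe rate but graded mild, and 46-60 is graded moderate.

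The mismatch therefore runs both ways: too strict for the youngest and too lenient for the oldest, taking Appendix 17.6 as the comparator.

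**Is the link to endpoints plausible?** Section 10.1.3.7 grades temperature, respiratory rate and SpO₂. Those are exactly the three items that Appendix 17.4 collects as numbers. The safety summaries in Section 11.1.6 do not use the grades; they report descriptive statistics and change from baseline. That makes an efficacy use the likely one, but it is an inference.

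**Source of the bands.** They follow the RSV Clinical Scoring System of Parts A and B (Appendix 17.1), except that its zero score is <30 rather than ≤30.

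**The case against.** The strongest reply is that the link is not written down. Section 10.1.3.7 sits under safety assessments, and Section 10.1.2.2 hands the choice of scales to the SAP. The SAP supplied (version 2.0) describes a different Part C, randomised 1:1 with about 120 subjects, so its silence on rate cut-offs says little about the current design. The Synopsis names heart rate as an RSV-related sign, yet Section 10.1.3.7 does not grade it, so that section is not a complete grading key. The Part C visit lists in Section 9.4 do not name respiratory rate among the signs, though they are worded as inclusive. Appendix 17.4 also records grunting and nasal flaring only as none or present, so not every listed sign has to have a moderate or severe grade. All of this stands, and it is why the endpoint consequence is conditional.

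It is also fair that the two instruments do different jobs. ReSVinet item 4 weighs persistence, response to suction or nebulisation, and effort; it can score severe at a normal or low rate. A number alone does not reproduce the item, so the conflict is between the numeric ranges, not between the whole item and the vital-sign bands.

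A reader might infer that young infants cannot resolve under this protocol, or that the treatment comparison is biased. The documents support neither. A reading of 30 or less would still count as normal at any age, and randomisation is stratified at 6 months, which limits imbalance between arms. What the reply does not remove is the stated analysis rule itself, or the missing definition of normalisation.

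**Conclusion.** The point holds as a should-fix, with medium confidence. It is certain that Section 10.1.3.7 and Appendix 17.6 give incompatible numeric normal ranges for Part C, completely so below 6 months, and that time to normalisation of respiratory rate is undefined. It is conditional that this harms the endpoints: that needs the Section 10.1.3.7 grades to define normal in the normalisation endpoint, or absent or mild in overall resolution and improvement.

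If they do, the expected effect is missed or delayed events in recovered young infants in all arms, which is a loss of sensitivity on secondary endpoints. Its size cannot be estimated, because the documents give no distribution of respiratory rates and Section 8.5.4 fixes no number per age stratum. The primary endpoint, time-weighted average change in viral load, does not use respiratory rate and is unaffected.

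**What to change.** Before Part C database lock and unblinding (Section 11.1 permits SAP amendments until then), reconcile Section 10.1.3.7 with Appendix 17.6 for the analysis:
- Replace the single normal cut-off with the upper bounds of the protocol's own Appendix 17.6 ranges: ≤50 under 2 months, ≤45 at 2 to <6, ≤40 at 6 to <12, ≤35 at 12 to <24, ≤30 at 24-36 months. Shared edges go to the older band, as the randomisation strata already do at 6 months.
- Apply it by age at each assessment. Age at screening would not do: the minimum age is 1 month (365.25/12 = 30.4 days) and Day 34 is 33 days after Day 1. The youngest child is then 30.4 + 33 = 63.4 days old, past 2 months (60.9 days), so every child enrolled under 2 months changes band during follow-up.
- Use the same definition for normalisation of respiratory rate and for the rate component of resolution.
- State in the SAP whether respiratory rate belongs to the set of signs behind overall resolution and improvement, and pre-specify the mild, moderate and severe split for improvement.

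The cost is protocol and SAP wording plus one derivation from rate and date of birth, both already collected. The downside is that Appendix 17.6 gives no numbers to separate mild from moderate. For 51-70, 46-60, 41-55, 36-50 and 31-40 (youngest to oldest band) that split is a convention. The severe rates are only orientative, and the normal cut-off drops by 5 breaths/min when a child crosses an age edge.

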10.1.3.8 Physical Examination

A full body physical examination will be performed at the time points specified in the relevant Schedule of Assessments for Part A (Table 1), Part B (Table 2) and Part C (Table 3a inpatients and Table 3b outpatients) in Section 8.1 and will include lung auscultation (wheezing during expiration/inspiration, crackles/crepitations), retraction of respiratory muscles, and general condition. Any changes from baseline will be recorded.

10.1.3.9 Electrocardiograms

A 12-lead ECG will be performed at Screening. Additional 12 lead ECGs will be performed at scheduled time points as indicated in the relevant Schedule of Assessments for Part A (Table 1), Part B (Table 2), and Part C (Table 3a inpatients and Table 3b outpatients) in Section 8.1.

10.1.3.10 Other Evaluations

Pulse Oximetry: Pulse Oximetry should be measured for all subjects without oxygen supply if deemed safe. When the SpO₂ is measured, always record the method of O₂ delivery, even if the SpO₂ is measured on room air. Any changes from baseline will be recorded.

Hydration Status: An evaluation of signs of dehydration according to the judgement of the Investigator should be performed ([Appendix 17.5](#) is to be used for reference) and recorded.

10.2 Data Safety Monitoring Committee

The DSMC will consist of medical advisers/monitors, pharmacokineticists, and biostatisticians. The DSMC will only include independent reviewers.

The DSMC will review all available safety and PK data collected

The specific responsibilities, composition of the DSMC, and the details of outputs provided for the review meeting are outlined in the DSMC Charter.

10.3 Appropriateness of Measurements

Assessments of the safety, efficacy, and PK measures planned for this study are widely used and generally recognised as reliable, accurate, and relevant to the disease condition.

11 STATISTICAL METHODS

11.1 Statistical and Analytical Plans

A statistical analysis plan (SAP) will be prepared by Syneos Health as a separate document. The SAP will include a more detailed description of the planned statistical methodologies for each part of the study. The SAP will be finalised before the closure of Part A. Any subsequent SAP amendments applicable to Parts B or C will be signed off prior to database lock and unblinding of the respective parts.

11.1.1 Datasets or Populations Analysed

The study populations include the Safety Population, PK Population, PD Population, and Efficacy Population.

Safety Population: defined as all subjects who received a single dose (Part A) or any part of any multiple dosing regimens (Parts B and C) of IMP (RV521 or placebo). The Safety Population is the primary population for the analysis of safety data. Analysis will be according to actual treatment received.

PK Population: defined as all subjects who receive IMP and have at least 1 post-dose PK concentration measured. The PK Population is the primary population for the analysis of PK data. Analysis will be according to actual treatment received.

Modified Intent-to-Treat (mITT) Population

The mITT Population is the primary population for the analysis of efficacy and PD data. Subjects will be analysed according to the randomised treatment. The mITT Population is defined as follows:

- In Part A, the mITT is defined as all subjects enrolled in the study who have an RT-qPCR viral load measurement and/or CBIA, if available, for at least 1 time point including baseline: pre-dose at Dosing Visit 1.
- In Part B, the mITT Population will include all subjects who received at least one dose of IMP (RV521 or placebo) and have a pre-treatment positive RSV nasopharyngeal swab confirmed by the central laboratory and agreed by the project team during the blind data review meeting. Potential inclusion of subjects who have not completed at least 6 doses of IMP will be decided by the project team during the blind data review meeting. Subjects will be analysed according to the randomised treatment.
- In Part C, the mITT Population will include all subjects who received at least one dose of IMP and have a pre-treatment positive RSV confirmed by the central laboratory.

Demographic and Other Baseline Characteristics: Demographic and baseline characteristics will be summarised descriptively by treatment. Quantitative variables will be summarised using the statistics n (number of observations), mean, standard deviation, median, minimum and

maximum. Qualitative variables will be summarised using n (number of subjects), absolute numbers and relative frequencies (%) per class.

